2.1.2. Primary evaluation criterion

- Haemoglobin level on day 5 post-operatively (considered the post-operative haemoglobin reference level in this study)
 - In the case of patients who received a transfusion postoperatively, the reference haemoglobin level will be the haemoglobin level at the end of hospitalisation
- Change in the Activities of Daily Living (ADL) score pre-fracture and 6 months post-operatively.
A loss of independence will be defined as a decrease of one point or more in the ADL.

The reference value for haemoglobin levels was arbitrarily set at 5 days post-operatively. This is because haemoglobin levels recorded in A&E or on admission to the ward prior to surgery, or immediately post-operatively, may be influenced by factors other than isolated anaemia. Dehydration, present in the emergency department or on admission to the ward before the operation, corrected preoperatively, and postoperative haemodilution due to fluid replacement, cause the haemoglobin level to vary without there being any real deglobulation. We therefore postulate that the haemoglobin level on the 5th postoperative day can serve as a reference.

Confounding factors collected

All confounding factors related to loss of autonomy will be collected:

- Transfusion and number of red blood cell concentrates received

The indication for transfusion is at the discretion of the prescriber. However, it is generally accepted to transfuse patients with haemoglobin levels below 8 g/dL, or below 10 g/dL in cases of ischaemic heart disease or poor clinical tolerance.

- Age
- Gender
- Height, weight, Body Mass Index (BMI) calculation
- Screening for past or present higher brain function disorders
- Screening for major sensory disorders
- Screening for depressive symptoms: Mini Geriatric Depression Scale (MiniGDS)
- Comorbidities assessed using the Cumulative Illness Rating Scale - Geriatrics (CIRS-G)
- ASA score
- Number of medications (per class) taken by the patient (anticoagulants, antiplatelet agents, NSAIDs, anti-osteoporotic drugs, analgesics)

- Lifestyle and living environment
- Severe fractures before and after inclusion
- Other falls during the year
- Protein-energy malnutrition
- Iron deficiency (ferritin < 30 µg/L or CRP > 20 mg/L associated with a transferrin saturation coefficient < 15%)
- Recurrence of falls at 1, 3 and 6 months post-op

2.2. *SECONDARY OBJECTIVES AND EVALUATION CRITERIA*

2.2.1. *Secondary objectives*

The secondary objectives are to analyse:

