- the influence of post-operative anaemia:
 - on independence in elderly patients who have undergone surgery for a fracture of the upper end of the femur upon discharge from hospital, at 1 month and 3 months post-operatively
 - on mortality 6 months after surgery
- the progression of post-operative anaemia

2.2.2. *Secondary evaluation criteria*

- Lowest postoperative haemoglobin level recorded on admission to the emergency department, on admission to the ward, on D0 (day of surgery), D1, D3, D5, D10 and D15 (postoperative days).
The severity of anaemia will be defined as follows:
 - greater than 12 g/dL,
 - less than or equal to 12 g/L
 - less than or equal to 8 g/L
 - less than 8 g/dL (and therefore requiring a transfusion)
- Assessment of Activities of Daily Living (ADL): pre-fracture, on day 5 post-operative (or on discharge from hospital if discharged before day 5) at 1 month, 3 months and 6 months post-operative.
- Assessment of instrumental Activities of Daily Living (IADL): pre-fracture, at 1 month, 3 months and 6 months post-operative.
Loss of independence will be defined as a decrease of one point or more in the ADL and/or IADL.
- Vital status at 6 months post-operatively

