5.2.1. Description of methods planned planned, including the schedule for planned interim analyses

All variables collected will be described by minimum, maximum, quartiles, mean and standard deviation for quantitative variables and by number and percentage of each modality for qualitative variables.

Analysis of the primary endpoint:

The relationship between loss of independence at 6 months and post-operative anaemia will be analysed using a logistic model. If a link is found, a multivariate analysis will be performed to confirm the independence of the anaemia/independence relationship. To do this, all potential confounding factors will be tested in a univariate analysis. Factors associated with a p value <0.20 will be retained in the multivariate model.

Analysis of secondary criteria:

- The analysis of the relationship between loss of autonomy on day 5 (or on discharge from hospital if discharged before day 5), at 1 and 3 months, and post-operative anaemia will be performed using the same method as for the primary endpoint.
- The 6-month mortality rate will be estimated with its 95% confidence interval using the Kaplan-Meier method.

The association between anaemia and mortality at 6 months will be studied using a Cox proportional hazards model in order to take confounding factors into account.

- The progression of post-operative anaemia (D0 to D15) will be described graphically.

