5.2.2. Statistical justification for the number of inclusions

According to data from the Medical Information Department (DIM) of the CHD in La Roche Sur Yon, over an inclusion period of 18 months, 320 patients aged over 75 underwent surgery on the upper end of the femur (210 patients per year, on average over the last 4 years of activity).

Assuming a mortality rate of 10% and a loss to follow-up rate of 10%, 255 patients could be analysed.

According to Gruson (20), 67.8% of patients regained their previous level of independence within 12 months, while 6.3% died within 6 months.

According to Halm (19), 65% of patients had post-operative anaemia of less than 10g/dL.

As the presence of at least 10 events (loss of independence) per criterion selected in the multivariate analysis is recommended, the inclusion of 255 patients appears to be consistent.

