5.2.3. Expected degree of statistical significance

The significance threshold is set at 5%.

5.2.4. Method of unused or invalid data into account of missing,

No imputation will be performed on missing data. These will be described in terms of numbers and percentages.

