5.2.5. Selection of individuals to be included in the analyses

All patients for whom preoperative and 6-month loss of autonomy is recorded will be included in the analysis.

6. **MONITORING AND MANAGEMENT OF ADVERSE EVENTS**

6.1. ***DEFINITIONS***

Vigilance	This refers to the monitoring of medicines, medical devices and other health-related products. It also consists of prevention of the risk of adverse effects resulting from their use, whether this risk is potential or proven,
Adverse events (AE)	Any harmful event occurring in a person participating in research involving human subjects, whether or not the event is related to the research or the product being researched.
Adverse effects (AE)	An adverse event occurring in a person participating in research involving human subjects, when this event is related to the research or the product being researched.
Serious Adverse Effects/Events (SAE)/(SAE)	Any adverse effect/event that: 
 * results in death, * is life-threatening, * causes temporary or permanent incapacitation or disability, * requires or prolongs hospitalisation of the patient, * causes a congenital or neonatal abnormality, * is medically significant (the list of medically significant effects/events is defined by the EMA).
Unexpected adverse effects (UEAEs)	Any adverse effect whose nature, severity or progression is inconsistent with the information relating to the products, procedures and methods used during the research.
New information	Any new data that could lead to a reassessment of the benefits and risks of the research or the product being researched, to changes in the use of this product, in the conduct of the research, or in the documents relating to the research, or to the suspension, interruption or modification of the research protocol or similar research. For trials involving the first administration or use of a health product in people who do not have any medical conditions: any serious adverse effect.
Abuse	Intentional, persistent or sporadic excessive use of a drug that is accompanied by harmful physical or psychological reactions.
Overdose	Administration of a quantity of a drug, given in a single dose or cumulatively, that is above above the maximum recommended dose according to the rules of

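### The independence result covers 6-month survivors only; the plan should say so and add a prespecified death-or-ADL-loss model beside it.

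*Combined protocol and SAP*

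**What the plan says.** The primary objective (section 2.1.1) concerns elderly patients operated on for a fracture of the upper femur. It does not restrict them to those alive at 6 months.

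The endpoint in section 2.1.2 is "Change in the Activities of Daily Living (ADL) score pre-fracture and 6 months post-operatively", dichotomised: "A loss of independence will be defined as a decrease of one point or more in the ADL". Neither sentence gives a patient who dies a value or a status.

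The sections that decide who is analysed come later:

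- Section 5.2.5: "All patients for whom preoperative and 6-month loss of autonomy is recorded will be included in the analysis".
- Section 5.2.4: "No imputation will be performed on missing data".
- Section 5.2.1: "The relationship between loss of independence at 6 months and post-operative anaemia will be analysed using a logistic model". Death is not mentioned for this model.
- Section 5.2.2: "Assuming a mortality rate of 10% and a loss to follow-up rate of 10%, 255 patients could be analysed". Deaths are subtracted before the analysable number is reached.

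Death is handled separately. Section 2.2.1 lists the influence of anaemia "on mortality 6 months after surgery" as a secondary objective. Section 5.2.1 plans a Kaplan-Meier estimate and a Cox model with confounders. The day-5, 1-month and 3-month independence analyses use the same method as the primary one.

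**The concern.** The question is put for everyone operated on, and the answer is computed in those who live 6 months and complete the call. A patient whose function falls and who survives is an event. A patient whose function falls equally and who dies before month 6 is absent from the 6-month result.

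This matters if death depends on the exposure. The plan gives some reason to ask: section 1.1 cites a cohort of 395 patients in which anaemia on admission went with higher 6- and 12-month mortality, and section 2.2.1 sets out to test the link. If anaemia contributes to death among the frailest, the anaemic patients left at 6 months are selectively robust, and the survivor comparison can make anaemia look less harmful than it is. Section 1.2.1 hopes to derive a standardised management protocol, including transfusion strategy, from this work. A weak or null result in survivors could then be read as applying to all operated patients.

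**Working it through.** **1. The plan's own figure.** The candidate count in section 5.2.2 is "320 patients aged over 75 underwent surgery on the upper end of the femur (210 patients per year, on average over the last 4 years". The yearly rate makes 315 over 18 months. Removing 10% deaths and 10% lost:

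- 320 × (1 − 0.10 − 0.10) = 256
- 315 × 0.90 × 0.90 = 255.15

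The stated 255 is reproduced, with the deaths subtracted. This agrees with sections 5.2.4 and 5.2.5.

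**2. How many deaths leave the result.** At 10%: 0.10 × 320 = 32. At the 6-month mortality of 6.3% cited in section 5.2.2: 0.063 × 320 ≈ 20.

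**3. Their share of bad outcomes.** Section 5.2.2 cites 67.8% regaining independence, so 32.2% did not. This is a 12-month figure from patients who, per section 1.1, were previously autonomous, living at home and cognitively intact. Expected losses: 0.322 × 255 ≈ 82.

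- 10% mortality: 32 / (32 + 82) ≈ 28%.
- 10% mortality, also counting expected losses among those lost to follow-up: 0.322 × 288 ≈ 93; 32 / (32 + 93) ≈ 26%.
- 6.3% mortality, 255 held fixed: 20 / (20 + 82) ≈ 20%. Letting the analysed number rise to 320 × 0.837 ≈ 268 gives 20 / (20 + 86) ≈ 19%; also counting those lost to follow-up gives about 17%.

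So the share is roughly 20 to 28%, a little lower on the last variants.

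**4. What a death-or-loss outcome could show.** Assumptions: 65% anaemic (section 5.2.2, below 10 g/dL), 32.2% loss among survivors in both groups (survivor odds ratio 1.00), and mortality ratio R for anaemic against non-anaemic patients. The documents give no R. With overall mortality m:

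- non-anaemic mortality d0 = m / (0.65R + 0.35); anaemic mortality d1 = R × d0
- composite risk = d + (1 − d) × 0.322

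For m = 0.10 and R = 2: d0 = 0.061, d1 = 0.121; risks 0.363 and 0.404; odds ratio 1.19.

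| Overall mortality | R = 1.5 | R = 2 | R = 3 |
|---|---|---|---|
| 6.3% | 1.07 | 1.12 | 1.18 |
| 10% | 1.11 | 1.19 | 1.28 |

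The survivor odds ratio is 1.00 in every cell by construction. The table shows what the survivor endpoint cannot see. It does not show bias in the ADL association.

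**5. Possible bias in the ADL association.** This needs a further assumption: a shared frailty that raises both death and ADL loss. With a standard normal frailty adding about 1 to both log-odds per standard deviation, 10 to 20% mortality and an anaemia odds ratio for death of 2 to 3, a true odds ratio of 1.00 appears as 0.96 to 0.90 among survivors, and a true 1.40 as about 1.36 to 1.27. The documents supply neither the frailty strength nor the odds ratio for death.

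**6. Precision, for scale.** With 255 patients split 65/35 and 32.2% events, expected events are about 53 and 29, and non-events about 112 and 61. SE(log OR) = √(1/53.4 + 1/112.4 + 1/28.7 + 1/60.5) ≈ 0.281, so the 95% interval around 1.00 is about 0.58 to 1.73.

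**The case against.** The strongest reply is that the death signal is already in the plan. The Cox model targets a mortality ratio of 1.5 to 3 directly, whereas the composite dilutes it to 1.11 to 1.28 at 10% mortality. That stands, and it is why the composite should not replace anything. It does not remove the gap: the two results are planned separately, and the independence result carries no survivor limit.

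Four stronger readings are tempting, and the documents do not support them.

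- A reader might take 1.11 to 1.28 as the bias in the primary result. These values come wholly from added deaths under assumed mortality ratios. The selection effects in step 5 are smaller, rest on further assumptions, and lie well inside the interval in step 6.
- A reader might infer that the plan expects anaemia to raise mortality. Section 2.2.1 poses a question. The cohort in section 1.1 concerns anaemia on admission, while section 2.1.2 sets pre-operative haemoglobin aside as a reference because dehydration distorts it. Section 1.1 also cites a review with no mortality difference, although it compared transfusion strategies and not anaemic with non-anaemic patients.
- A reader might say that a patient who dies at month 4 contributes nothing. That patient counts in the Cox model and, unless section 5.2.5 governs every analysis, in the earlier ADL analyses.
- A reader might quote 28% alone. It sets deaths among 320 against losses among 255 and uses the higher mortality figure.

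It is also fair that a composite mixes death with dependence. If mortality is unrelated to anaemia, it weakens a real effect: at 10% mortality, a survivor odds ratio of 1.50 becomes 1.39.

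**Conclusion.** The point holds as a gap between the objective and the analysis set. Sections 5.2.4 and 5.2.5 together make the primary analysis survivor-only, section 2.1.1 does not, and nothing in the plan bridges the two. About 20 to 32 expected deaths leave the independence result, roughly 20 to 28% of patients who die or lose independence. This rests on 320 candidates, 6.3 to 10% mortality and a loss rate borrowed from a fitter cohort at 12 months.

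That the survivor-only association may understate harm is conditional on a link between anaemia and death. Neither the size nor the direction of any bias can be established from the documents. Confidence is high on the restriction to survivors and low on its numerical effect. The change is worth making because it is cheap and must be fixed before results are seen.

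**What to change.** Keep the ADL endpoint as primary, and make three changes.

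1. In sections 2.1.2, 5.2.1 and 5.2.5, state that the primary result applies to patients alive at 6 months with a recorded ADL.
2. In section 5.2.1, prespecify one companion logistic model with the same exposure and covariates, at 6 months and also at months 1 and 3. The outcome is death by that time point or a fall of one ADL point or more. The population is patients with a reference haemoglobin and a pre-fracture ADL who either died or have an ADL at that time point. For patients alive, or of unknown vital status, without an ADL, show bounds counting all of them as events and then all as non-events. Taking every known-alive patient without an ADL as simply unclassified would over-weight death, because deaths can always be scored.
3. Report the companion result and deaths by haemoglobin level beside the primary result. No rule that the two analyses must agree is needed.

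On the plan's figures the companion model has about 114 events in 255 + 32 = 287 patients (39.8%). With a further 32 patients lost, the bounds on the event proportion would run from 114/319 ≈ 36% to 146/319 ≈ 46%.

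Vital status is already recorded at each contact (section 4.1), so no new data or visits are needed. The cost is one extra model per time point with its bounds, and a composite that mixes death with dependence and dilutes the effect if mortality is unrelated to anaemia. It therefore supplements the primary analysis and does not replace it.

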4.3. DESCRIPTION DETAILED OF THE EVALUATION AND THE DATA COLLECTED

a. On patient autonomy:

- **Activities of Daily Living (ADL)** (21): Measured at inclusion (information relating to the week preceding the procedure) (questioning of patient, family, nursing home staff), on day 5 post-op (or on discharge from hospital if discharged before day 5) (*in hospital*), 1 month, 3 months and 6 months post-op (*telephone call*).

Validated scale for assessing independence in simple activities of daily living: hygiene, dressing, mobility, going to the toilet, continence, eating. Each item is coded as follows:

1: done independently

0.5: done partially or with assistance

0: not done

Scale ranging from 0 to 6, with a high score indicating a more independent patient.

- Lawton's 4-item **Instrumental Activities of Daily Living (IADL)** (22): Measured at inclusion (information relating to the week preceding the intervention) (questioning of patient, family, nursing home staff), at 1 month, 3 months and 6 months post-operatively (*telephone call*).

Validated scale for assessing patient autonomy in so-called "instrumental" activities of daily living: managing finances, preparing medication, using the telephone, using transport. Each item is coded as follows:

1 : done alone

0.5: does partially or with assistance

0: does not do

The score ranges from 0 to 8. A high score indicates that the patient is independent. This score can only be interpreted for subjects living at home.

- **Cumulative Ambulation Score** (23): Measured at inclusion (information relating to the week preceding the procedure), from D1 to D3 post-operative, on D5 post-operative (or on discharge if before D5) (*in-hospital*), and at 1 month, 3 months and 6 months (*telephone call*)

Validated score predictive of mortality, morbidity and rehabilitation. Three areas (transfer from lying to sitting, transfer from sitting to standing, walking with appropriate aids) are assessed from 0 (unable despite the help of two people) to 2 (able to do independently). The scores are cumulative over the first 3 days post-operatively and give a score of 0 to 18. A cumulative score greater than 10 corresponds to a 99% probability that the patient will be alive at one month, 93% that they will have returned home, and 94% that they will not have had any major post-operative complications.

b. On the patient's physical performance:

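### Month-6 independence is modelled only as a yes/no fall of one ADL point; a pre-specified baseline-adjusted analysis of the full score, and a repeat in patients able to show the fall, would be a cheap improvement

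*Combined protocol and SAP*

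**What the plan says.** Section 2.1.2 names the outcome as "Change in the Activities of Daily Living (ADL) score pre-fracture and 6 months post-operatively" and then turns it into a yes/no event: "A loss of independence will be defined as a decrease of one point or more in the ADL".

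Section 4.3.a describes the scale: "Scale ranging from 0 to 6, with a high score indicating a more independent patient". There are six items, each scored 1, 0.5 or 0, the middle level being "0.5: done partially or with assistance". The total can therefore take 13 values.

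Section 5.2.1 gives the model: "The relationship between loss of independence at 6 months and post-operative anaemia will be analysed using a logistic model". The analyses at day 5, month 1 and month 3 "will be performed using the same method as for the primary endpoint". No model of the ADL score or of its change is planned. The score itself would appear only in the descriptive tables: "All variables collected will be described by minimum, maximum, quartiles, mean and standard deviation for quantitative variables".

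Sections 3.2 and 3.3 set no minimum pre-fracture ADL, and sections 4.1 and 4.4 expect care-home residents and patients with dementia. Section 5.2.5 analyses everyone with a preoperative and a 6-month value. Pre-fracture ADL is not in the list of confounders in section 2.1.2, although section 1.1 reports low previous independence as one of the strongest risk factors.

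**The concern.** There are two separate issues.

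**Precision.** A fall of 1 point and a fall of 6 points count the same, and a fall of half a point counts as nothing. The study is modest in size: about 82 events at the rate cited in section 5.2.2, with no power or effect size stated. No margin is therefore shown to absorb a loss of information. Section 5.2.1 also fits the multivariable model only if the first logistic model finds a link, so a blunt outcome at that step can stop the adjusted analysis from being run.

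**Patients who cannot have the event.** A patient can fall by no more than the starting score. Anyone starting at 0 or 0.5 cannot lose a full point, but stays in the analysis set and is coded as having kept independence. These are non-events by construction and say nothing about whether anaemia affects recovery.

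**Working it through.** **1. The plan's own figures.** Section 5.2.2 gives 320 patients in 18 months (210 per year), 10% deaths, 10% lost to follow-up, and 255 analysable.
- 320 × (1 − 0.20) = 256
- 320 × 0.9 × 0.9 = 259.2
- 210 × 1.5 × 0.9 × 0.9 = 255.15

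The 255 reproduces. The section also cites that "67.8% of patients regained their previous level of independence within 12 months", so the implied loss rate is 1 − 0.678 = 0.322. Expected events are 255 × 0.322 = 82, or about 8 model terms at 10 events each.

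**2. Information kept, normal change.** If the change is normal and haemoglobin shifts it linearly, a cut with event rate p keeps R = φ(z_p)² / [p(1 − p)].
- At p = 0.322: z = 0.462 in absolute value and φ = 0.3585, so R = 0.1285 / 0.2183 = 0.589. Then 255 × 0.589 = 150 patients.

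| Loss rate p | R | Equivalent patients of 255 |
|---|---|---|
| 0.20 | 0.49 | 125 |
| 0.25 | 0.54 | 137 |
| 0.322 | 0.59 | 150 |
| 0.40 | 0.62 | 159 |
| 0.50 | 0.64 | 162 |

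The loss rates other than 0.322 are assumptions. The upper end reflects section 1.1, where nearly half of a cited cohort had not regained independence at one year.

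**3. Information kept, against a proportional-odds model.** For small effects and many levels, R ≈ 3p(1 − p).
- p = 0.20: 0.48
- p = 0.322: 3 × 0.322 × 0.678 = 0.655, or 167 of 255
- p = 0.50: 0.75

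Ties in the real score raise these shares somewhat.

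**4. Check with a bounded half-point score.** Month-6 ADL was simulated as baseline plus a mean shift, a haemoglobin effect and normal noise, rounded to half points and held within 0 to 6. R is the ratio of squared correlations with haemoglobin (binary loss over change score), with and without baseline adjustment. The baseline distributions are assumed.

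| Assumed baseline | R |
|---|---|
| Most near the ceiling | 0.66–0.74 |
| Intermediate | 0.62–0.68 |
| Uniform over 13 levels | 0.55–0.60 |

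Simulated loss rates ran from 28% to 50%.

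**5. What it means for power.** Take, for illustration, an effect with 80% power on the full scale (two-sided 5%). Power on the binary scale is Φ[(1.96 + 0.84)√R − 1.96].
- R = 0.49: 2.80 × 0.700 − 1.96 = 0.00, about 50%
- R = 0.589: 2.80 × 0.767 − 1.96 = 0.19, between 57% and 58%
- R = 0.75: 2.80 × 0.866 − 1.96 = 0.46, about 68%

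**6. The floor.** The largest possible fall equals the baseline score.
- Baseline 0: largest fall 0. No analysis of survivors' ADL can show a loss.
- Baseline 0.5: largest fall 0.5. The full score can show it; the one-point rule cannot.
- Baseline 1: largest fall 1, so the event is possible.

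The documents give no pre-fracture ADL distribution, so the share below 1 cannot be computed.

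**The case against.** The one-point loss is pre-specified and easy to read clinically, and the events-per-variable argument in section 5.2.2 is built on it. Month-6 ADL is taken by telephone from the patient, family or care-home staff (section 4.5), so ignoring half-point changes may be a sensible guard against informant noise. The efficiency formulas treat every half point as signal. This stands, and it is why the binary result should remain the headline.

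Four stronger readings are tempting, and the documents do not support them.

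- *That 41% of the information is lost.* The 0.59 needs a normal change and a loss rate of 32.2%. That rate is a 12-month figure from a cohort which section 1.1 describes as previously autonomous, living at home and without cognitive impairment. It is not a 6-month rate of one-point ADL loss in this broader population. Only a range can be defended.
- *That the cut-off hides loss in everyone starting below 1.* It does so only at 0.5. At 0 the scale itself has no room.
- *That the floor biases the association toward or past the null.* This would need patients with very low ADL to be more anaemic and numerous enough to matter. The documents show neither.
- *That deaths should be ranked as the worst outcome in the same model.* Section 5.2.5 analyses patients with both ADL values, and section 5.2.1 handles mortality separately by a Cox model. Ranking death would change the question, and the efficiency argument gives no reason for it.

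**Conclusion.** This is a cheap improvement. The primary analysis is neither invalid nor contradictory.

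Two things are established from the documents. A 13-level score is modelled only as a yes/no fall of one point or more. Patients starting at 0 or 0.5 are eligible, cannot have the event, and remain in the analysis as non-events.

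The retained information is roughly 50 to 75%, equivalent to about 128 to 191 of 255 patients (255 × 0.50 and 255 × 0.75) analysed on the full score. That range assumes loss rates of about 20 to 50% and a haemoglobin effect that acts as a shift along the scale. If half-point changes are largely noise, the real gain from the full score would be smaller. The size of the floor effect and the direction of any bias are unknown.

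**What to change.** Leave the one-point loss as the headline result and add the following to section 5.2.1 before the data are analysed:

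1. A supportive proportional-odds model (or a linear model) of month-6 ADL on the same haemoglobin variable as the primary analysis. Adjust it for pre-fracture ADL and the same confounders, in patients with both ADL values. Fit it whatever the primary model shows.
2. A repeat of the binary analysis restricted to patients with a pre-fracture ADL of at least 1.
3. A count of patients with a pre-fracture ADL of 0 and of 0.5, reported with the pre-fracture distribution.

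If the investigators want an analysis that ranks death as the worst level, it should be at most a separate, labelled sensitivity analysis.

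The cost is one or two extra estimates to report and a check of the proportional-odds assumption. All the data are already collected, so no visits, patients or measurements are added. Naming the models in advance also avoids a data-driven choice between scales later, and helps show whether a null result reflects no association or a coarse outcome.
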